4.4 Treatments

4.4.1 Treatments Administered

All participants will receive a single oral dose of pretomanid 200 mg in the form of a tablet.

4.4.2 Identity of Investigational Product(s)

Pretomanid, a nitroimidazooxazine, is a chemical entity with a molecular weight of 359 Daltons. Pretomanid is a novel TB treatment that is being investigated for use with other TB drugs to shorten and/or simplify regimens to treat either drug-susceptible or resistant disease, which may improve the current high rate of noncompliance for TB treatment. Pretomanid acts by inhibiting Mtb cell wall biosynthesis, as well as generating NO.

For this study, pretomanid 200 mg tablets are white to off-white, oval-shaped tablet debossed with M on one side and P200. The formulation of pretomanid tablets includes 200 mg of micronized pretomanid, 294.4 mg of lactose monohydrate National Formulary (NF) (Foremost FastFlo 316), 235.2 mg of microcrystalline cellulose NF (Avicel PH102), 40 mg sodium starch glycolate NF (Explotab), 8.0 mg magnesium stearate NF (Hyqual), 2.4 mg of colloidal silicon dioxide NF (Cab-O-Sil M-5P), 4 mg of sodium lauryl sulfate United States Pharmacopeia (USP), and 16 mg of povidone USP (PVP K30). There is also purified water USP that is removed during manufacture. All study product, pretomanid tablets, should be stored at 15-30°C (59-86°F) in blister-strips comprising a thermoformable-film and a lidding foil configuration.

The TB Alliance or its designee will package the study product. The study product will be labeled and supplied according to applicable regulatory requirements. Pretomanid will be provided by Global Alliance for TB Drug Development according to the terms of the Clinical Trial Agreement between the TB Alliance and NIAID.

4.4.3 Method of Assigning Participants to Impairment Groups

There is no randomization performed for this open-label study. Participants are assigned to the 3 renal impairment groups based on their MDRD eGFR, with approximately 6 participants per renal impairment group (Groups 2, 3, and 4) and approximately 18 healthy participants will be matched to 1 or more renal impairment participants (Groups 1A, 1B, and 1C).

Enrollment will be performed through the enrollment module in the electronic data capture system, maintained by the SDCC.

4.4.4 Selection of Doses in the Study

Data from the Phase 1 studies in healthy volunteers and Phase 2 studies in participants with pulmonary TB indicate that the PK profile for pretomanid following oral dosing was consistent for healthy participants and participants with pulmonary TB. In both populations, pretomanid was readily absorbed after oral administration and slowly eliminated from plasma. Pretomanid plasma concentrations increased in a dose-dependent manner after single-dose administration of up to 1000 mg in healthy participants and participants with TB, but the increase was less than dose proportional, particularly at doses above 200 mg/day. Evidence suggests that the apparent lack of dose proportionality in exposure is most likely related to decreased bioavailability with increasing dose. The clinical dose is 200 mg and it is recommended that pretomanid be administered in the fed state.

4.4.5 Selection and Timing of Dose for Each Participant

Pretomanid will be administered in the fed state in this study because there is a food effect for the drug. Following an overnight fast of at least 8 hours, participants should start the recommended meal prior to administration of pretomanid [40] on study day 1. Study participants should eat this meal in 30 ± 10 minutes or less; however, pretomanid should be administered 30 ± 10 minutes after start of the meal. Participants will be given one dose of 200 mg of pretomanid orally under direct supervision with 240 mL of water and a mouth check will be done at visit 01A. All participants will receive the same study product. After dosing, participants will have no food, water, or medications for 2 hours post-dose. If a participant vomits >2 hours post-dose, no redosing or exclusion is required. If a participant vomits within 2 hours of dosing, the participant will be excluded from the study with a plan to replace or rescreen and admit another time, if necessary. Since a single oral dose of pretomanid will be given, there will be no dose modifications.

4.4.6 Blinding

Not Applicable; this is an open-label study.

4.4.7 Prior and Concomitant Therapy

Medications history will include a review of all current medications and medications as specified in Table 4 of the protocol. Assessment of eligibility will include a review of all permitted and prohibited medications per the participant inclusion and exclusion criteria. In addition, the site PI or appropriate sub-investigator may identify other medications that should not be used due to a risk to participant safety or possible effects on PK parameters. Accordingly, specific interactions should be checked using a drug interaction program such as the Lexicomp drug interactions program included within UpToDate. Administration of any medications, therapies, or vaccines will be recorded on the appropriate Data Collection Form (DCF). Concomitant medications will include all current medications and medications taken in the 30 days prior to signing the informed consent form (ICF) through approximately 11 days after the study medication is given, early termination (ET) or unscheduled visits (if prior to 11 days after study product administration), whichever

occurs first. Medications reported are limited to those taken within 30 days prior to the study medication through approximately 11 days after the study medication. Prescription and over-the-counter drugs will be included as well as vitamins, and supplements (including herbal).

4.4.8 Treatment Compliance

All participants are to receive a single dose of study product administered under supervision in the clinic including a post-administration mouth check.

4.5 Pharmacokinetic and Safety Variables

See [Table 2](#) for a schedule of study procedures.

4.5.1 Pharmacokinetic Variables

The plasma PK of a single dose of pretomanid will be assessed from serial blood samples collected up to 1 hour pre-dose (Day 1) and at multiple time points post dosing: 1, 2, 4, 5, 6, 8, 12, 16, 24, 36, 48, 72, and 96 hours. The primary outcome measure will be total plasma concentration of pretomanid. The following PK parameters will be determined using total pretomanid and metabolites M19 and M50 concentrations:

C_{max} : Maximum plasma concentration

T_{max} : Time to peak (maximum) plasma concentration

AUC_{last} : Area under the plasma concentration-time curve from time zero to time of last measurable concentration

AUC_{∞} : Area under the plasma concentration-time curve from time zero to infinity

$\%AUC_{ex}$: Percentage of AUC_{∞} obtained by extrapolation

$t_{1/2}$: Terminal-phase elimination half-life

λ_z : First-order terminal elimination rate constant

CL/F : Apparent clearance

V_d/F : Apparent terminal phase volume of distribution

The urine PK of a single dose of pretomanid will be assessed from urine collected up to 1 hour pre-dose, 0-4, 4-8, 8-12, 12-24, 24-48, 48-72, and 72-96 hours post-dose. The following PK parameters will be determined using urine volumes and concentrations for pretomanid and the metabolites M19 and M50:

$Ae_{(0-t)}$: Cumulative amount excreted into the urine from time 0 to the time t

$Ae\%Dose$: Fraction of dose excreted into the urine

CL_R : Renal clearance

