unmetabolized pretomanid is excreted in the urine. [18]. Therefore, like other commonly used anti-TB drugs such as ethambutol and pyrazinamide, which are at least partly eliminated through kidneys, the PK of pretomanid must be studied in patients with CKD. CKD is a very common clinical disease with estimated prevalence of 8 to 16%, and CKD patients globally, particularly those in advanced stages, have significantly increased risk of developing TB [11-13].

Regarding pretomanid metabolites, no single metabolic pathway can be considered major. Two metabolites have been selected for quantification: M19 (4-Trifluoromethoxybenzoic acid) and M50 (hydroxy imidazole). In one mass-balance study, M19 was the largest drug-derived metabolite, representing up to 35% of the sample radioactivity at 24 hours post-dose. However, it has no activity or toxicity. In another mass-balance study, M50 was found to account for 6.3% of the parent area under the AUC and it has been identified as potentially genotoxic based on an in vitro Ames test. In 2 mouse genotoxicity studies, no genotoxicity was observed up to a 2000 mg/kg dose. In a recently completed carcinogenicity study in transgenic mice with M50 exposure 2-3 times the expected human exposure, no pretomanid-related deaths, tumors, or gross necropsy findings were seen. There is no evidence suggestive of any potential carcinogenic hazard in rat toxicity studies up to 6 months and in monkey toxicity studies up to 9 months. No metabolites have been found to represent more than 13% of the total dose in urine and feces. Therefore, based on results from previous studies and expected excretion in urine, measuring the plasma exposures of pretomanid metabolites (M50 and M19) in this patient population will be valuable.

The results from this study will help determine future dosing and frequency of administration of pretomanid that can be safely used in patients with different stages of renal impairment.

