3.3.1 Pharmacokinetic Parameter Definitions

Maximum plasma concentration (C_{max}) is defined as the maximum observed concentration, occurring the time of maximal plasma concentration (T_{max}), in plasma following the first dose of pretomanid.

Time of maximum plasma concentration (T_{max}) is defined as the time at which the maximum observed plasma concentration occurs. Because non-steady-state data is collected, the entire curve is considered. If the maximum observed concentration is not unique, then the first maximum is used.

Elimination rate constant (λ_z) is defined as the first-order rate constant associated with the terminal (log-linear) portion of the curve describing the rate of elimination from plasma. Estimated by linear regression of time vs. log concentration.

The terminal elimination half-life ($t_{1/2}$) is defined as the time it takes plasma concentrations to reduce by 50% during the terminal elimination phase and will be estimated by the natural logarithm of 2 ($\ln(2)$) divided by λ_z .

AUC_{last} is defined as the area under the concentration-time curve (AUC) from the time of dosing to the time of the last quantifiable concentration above the lower-limit of quantitation (LLOQ) based on observed concentrations.

C_{last} is defined as the last observed positive concentration above the LLOQ.

AUC_{∞} is defined as the AUC from the time of dosing extrapolated to time infinity based on C_{last} . It will be computed by adding AUC_{last} to an area extrapolated by C_{last} divided by λ_z , as shown below:

$$AUC_{\infty} = AUC_{last} + \frac{C_{last}}{\lambda_z}$$

% AUC_{ex} is defined as the percentage of AUC_{∞} that was extrapolated and is calculated as shown below:

$$\%AUC_{ex} = 100 \times \left(\frac{AUC_{\infty} - AUC_{last}}{AUC_{\infty}} \right)$$

Apparent oral clearance (CL/F) is defined as the apparent total body clearance and represents a volume that is cleared of the molecule of interest per hour. It will be calculated as the dose divided by the AUC_{∞} , as shown below:

$$\frac{CL}{F} = \frac{Dose}{AUC_{\infty}}$$

Apparent volume of distribution during the terminal phase (V_z/F) is defined as the theoretical volume that the total amount of the molecule of interest would occupy if uniformly distributed at the concentration observed in plasma. If the terminal phase has been adequately captured, this value should approximate the volume of distribution at steady state and is calculated as shown below:

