$$\frac{V_z}{F} = \frac{Dose}{\lambda_z \times AUC_{\infty}} = \frac{CL}{\lambda_z \times F}$$

$Ae_{(0-t)}$ is defined as the total amount of drug excreted unchanged, or amount of metabolite, in urine over the time interval 0 to time t. It is calculated as the sum of all the concentrations measured in the urine samples pooled over each interval multiplied the total respective volume of each urine sample.

%AeDose is represent the percent of the dose that was excreted unchanged in urine. It is calculated as the shown below:

$$\%AeDose = \frac{Ae_{(0-t)}}{Dose}$$

The renal clearance (CL_R) is defined as the clearance attributable to the renal route. Its calculation requires both urine and non-urine (typically plasma) data to be collected from the same route and regimen in the same individuals. It can then be estimated as the amount excreted in urine divided by the observed AUC in the non-urine matrix over the equivalent time interval as the urine data was collected, as shown below:

$$CL_R = \frac{Ae_{(0-t)}}{AUC_{(0-t)}}$$

Where $Ae_{(0-t)}$ is the amount excreted in urine and $AUC_{(0-t)}$ is the AUC in the non-urine matrix.

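### SAP 4.5.1 gives M19 and M50 a CL/F, Vd/F and Ae%Dose, but the only formulas use the parent dose: the metabolite clearance and volume are mislabelled, and M19 percent of dose is 1.74-fold low if M19 is reported as its own mass

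*SAP*

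**What the plan says.** SAP 4.5.1 introduces the plasma list, which includes CL/F and Vd/F, with "The following PK parameters will be determined using total pretomanid and metabolites M19 and M50 concentrations". It introduces the urine list, which includes Ae%Dose, with "The following PK parameters will be determined using urine volumes and concentrations for pretomanid and the metabolites M19 and M50". The same lists in SAP 3.2.1.1 and 3.2.1.2 are for pretomanid only.

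SAP 10.2.2.1 and 10.2.2.2 send the analyst to SAP 3.3.1 for definitions. The formulas there are:

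- CL/F = Dose/AUC∞, where CL/F "is defined as the apparent total body clearance and represents a volume that is cleared of the molecule of interest per hour"
- Vz/F = Dose/(λz × AUC∞)
- %AeDose = Ae(0-t)/Dose

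The only dose in the study is 200 mg of pretomanid (SAP 4.4.1). Ae is defined to cover the "total amount of drug excreted unchanged, or amount of metabolite, in urine over the time interval 0 to time t", computed as concentration times volume. The next definition then says "AeDose is represent the percent of the dose that was excreted unchanged in urine". SAP 4.5.1 describes the same quantity as "Fraction of dose excreted into the urine".

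Protocol 10.5.4 asks for plasma AUClast of M19 and M50, leaves room for further plasma parameters, and asks for urinary excretion. Adding metabolite parameters is therefore allowed.

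**The concern.** The formulas were written for the drug that was swallowed. Applied to a metabolite, they raise three problems.

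1. Dividing the parent dose by a metabolite AUC mixes how much metabolite was formed with how fast it is cleared. A lower value in the severe group could mean slower elimination or greater formation, yet the label says clearance.
2. Dividing milligrams of M19 by milligrams of pretomanid is not a percentage of the dose, because the two molecules differ in weight.
3. A metabolite cannot be drug excreted unchanged, so the percentage definition does not fit an Ae that includes metabolites.

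A separate slip affects every analyte: one section says fraction, the other says percent, and the formula has no factor of 100.

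At stake are the absolute metabolite values in the study report. Protocol 2.2.1 itself quotes metabolite recovery as a percentage of dose, so readers would have a benchmark to set an M19 figure against. Protocol 10.1 also says that Part B, if run, aims to estimate parameters of the parent and the metabolites and relate them to renal function.

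**Working it through.** The plan states no value for M19 or M50 CL/F, V/F or percent of dose, so there is no figure to reproduce. The check applies the SAP's formulas to a metabolite.

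**Inputs**

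- Dose 200 mg (SAP 4.4.1); pretomanid molecular weight 359 (SAP 4.4.2).
- Identity of the metabolites: "M19 (4-Trifluoromethoxybenzoic acid) and M50 (hydroxy imidazole") (Protocol 2.2.1). The name of M19 gives C8H5F3O3. Its weight is not printed and is derived here. The description of M50 is too general to give a weight.
- Ceiling for illustration: "No metabolites have been found to represent more than 13% of the total dose in urine and feces" (Protocol 2.2.1), taken here as a molar percentage.
- Fraction formed (fm): not given; assumed 0.05 to 0.5.

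**Percent of dose for M19**

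Molecular weight: 8 × 12.011 + 5 × 1.008 + 3 × 18.998 + 3 × 15.999 = 206.12.

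Ratio: 359/206.12 = 1.742; inverse 0.574. If 359 is a rounded figure, the ratio lies between 1.739 and 1.744.

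This takes one M19 per pretomanid. Two trifluoromethoxybenzyl units at about 175 each would leave only about 9 of the 359, so a second M19 from the same molecule is not plausible.

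At a true 13%: 0.13 × 200 = 26.0 mg pretomanid equivalents; 26.0 × 0.574 = 14.93 mg of M19; 14.93/200 = 7.46%. The gap is 13 − 7.46 = 5.54 points.

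| True molar recovery | Printed if M19 is reported as its own mass |
|---|---|
| 1% | 0.57% |
| 5% | 2.87% |
| 10% | 5.74% |
| 13% | 7.46% |

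If all 200 mg became urinary M19, the formula would give 57.4% rather than 100%. If the laboratory reports parent equivalents, the printed and true values agree.

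**CL/F and V/F for a metabolite**

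In molar terms the amount of metabolite formed is F × fm × Dose, so AUC∞ of the metabolite = F × fm × Dose/CL_m. Hence Dose/AUC∞ = CL_m/(F × fm), which exceeds CL_m/F by 1/fm. V/F carries the same factor.

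| Assumed fm | Printed ÷ (CL_m/F), molar | M19 as its own mass (× 1.742) |
|---|---|---|
| 0.05 | 20 | 34.8 |
| 0.10 | 10 | 17.4 |
| 0.20 | 5 | 8.7 |
| 0.50 | 2 | 3.5 |

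The protocol's own figures give an example for M50. Parent CL/F of about 8 L/h (Protocol 2.1.5.2) implies a parent AUC∞ of 200/8 = 25 µg·h/mL. M50 at 6.3% of parent AUC (Protocol 2.2.1), read as a mass-based AUC∞ ratio, is 0.063 × 25 = 1.575 µg·h/mL. The labelled M50 CL/F would be 200/1.575 = 127 L/h. That is 8/0.063, the parent value divided by the AUC ratio, and it does not separate M50 clearance from M50 formation.

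**The case against.** The strongest reply is that the 1.74 rests on facts outside the documents. The laboratory's reporting basis is not stated, the weight of M19 is derived from its name, and M50 has no factor at all. The clearance multiples are 1/fm over an assumed range. The 13% ceiling covers urine and feces together and any metabolite, so urinary M19 may be well below it. All of this stands, and it limits the size of the error. It does not supply a formula that works for a metabolite.

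A second reply is that apparent clearance already carries an unknown F, so fm is merely one more unknown scale, and relabelling as CL/(F × fm) would do. Relabelling would indeed be an acceptable alternative. As the text stands, however, the SAP defines the quantity as clearance of the molecule concerned, and that fails for a metabolite on any reporting basis.

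Third, the named metabolite outcomes in SAP 3.2.2 are plasma AUClast, with room for other plasma parameters, and urinary amounts, and the parameter table shells name no metabolite. That makes 4.5.1 look over-broad, but it does not cancel what 4.5.1 says will be determined.

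Fourth, a conversion might sit in the separate NCA template or in the software set-up. Appendix 4 refers to the template only if applicable, and the SAP cites no conversion step.

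**Conclusion.** The concern holds, at low severity. Under the formulas as written, CL/F and V/F for M19 and M50 would not be what their labels say, whatever the reporting basis. The M19 percent of dose would be 1.74-fold too low if M19 is reported as its own mass, which is at most about 5.5 percentage points at the 13% ceiling. It would be correct, apart from the missing factor of 100, if M19 is reported as parent equivalents. The 1.74 assumes the weight derived from the name and one M19 per pretomanid; the clearance multiples also depend on the assumed fraction formed.

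The effect is confined to absolute values of descriptive secondary parameters. A constant factor cancels in impaired-to-control ratios of Ae%Dose. Ae itself, renal clearance, metabolite AUC, all pretomanid parameters used in the group comparison and the Part B decision are untouched. The ANOVA in SAP 10 covers AUClast, AUC∞ and Cmax only, and no recovery sum across analytes is planned.

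**What to change.** In SAP 4.5.1, limit CL/F and Vd/F to pretomanid.

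In SAP 3.3.1:

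- For concentrations reported as analyte mass, define Ae%Dose = 100 × (Ae/MW of analyte)/(Dose/MW of pretomanid). For parent equivalents, use 100 × Ae/Dose.
- Remove the word unchanged where the definition applies to metabolites.
- State the laboratory's reporting basis for M19 and M50 and, if it is analyte mass, their molecular weights.

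Use percent in both sections.

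The plasma and urine subsets in SAP 6.3.2.1 and 6.3.2.2 are defined by the 4.5.1 lists, so narrowing the plasma list will also tighten the plasma subset definition; check that this is intended.

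The cost is SAP wording and, if concentrations are in analyte mass, one constant per metabolite in the program. No new data or assays are needed.

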4.5.2 Safety Variables

The incidence, frequency, and severity of AEs, TEAEs, and SAEs. In addition, the mean change from baseline in the following variables:

- HgB
- ALT
- AST

- BUN
- Creatinine and eGFR
- Serum potassium and magnesium
- Oral temperature
- Pulse
- Sitting blood pressure
- ECG QTcF

5 SAMPLE SIZE CONSIDERATIONS

A sample size of 6 per group is standard for renal impairment PK studies. Prior studies of pretomanid (PA-824) with similar dosing (200 to 250 mg) have estimated coefficients of variation (CV) of 16% to 33% for the AUC after a single dose in healthy adult participants. Assuming a 20% CV for the AUC of both groups, the probability of observing at least a 50% increase in the geometric mean ratio of AUCs given a true 100% increase is >99%. The probability of the lower bound of the 90% CI for the geometric mean ratio of AUCs being at least 1.5 in this scenario is approximately 70%.

The sample size per arm in Part B was chosen based on feasibility and appropriateness for a PK study in renal impaired participants to estimate group differences in PK parameters with adequate precision. Assuming an observed 2-fold difference between each renal impairment group and matched controls with no correlation between matched pairs and a coefficient of variation of 20%, a 90% CI for the fold difference between groups is (1.70, 2.35).

6 GENERAL STATISTICAL CONSIDERATIONS

6.1 General Principles

There are several units of analysis in this study. For the PK analysis, the unit of analysis will be the reported pretomanid concentrations, however, PK profiles in both plasma and urine will be evaluated at the participant level. Medical history, concomitant medications, AEs, SAEs, clinical laboratory, physical examination (PE), vital signs, and ECG will be presented at the participant level, and summaries will be presented at the study and renal impairment group level.

All continuous variables will be summarized using the following descriptive statistics: n (non-missing sample size), arithmetic mean, standard deviation (SD), median, minimum (min), and maximum (max). PK concentration and parameter summaries will additionally report the geometric mean (GM) and coefficient of variation (CV). Minima and maxima will be reported to the same precision as the raw values, means and medians will be presented to one extra decimal place than the raw values and standard deviations will be reported to 2 extra decimal places than the raw values.

The frequency and percentages (based on the non-missing sample size) of observed levels will be reported for all categorical measures. Percentages will be rounded to one decimal place (i.e. XX.X%) except for 100% which will be reported with no decimal places. In general, all data will be listed, sorted by impairment group and participant, and when appropriate by visit number and parameter within participant. In general, the last recorded value prior to study drug administration will be considered as baseline. Changes from baseline will be calculated as the follow-up visit value minus the corresponding baseline value. All summary tables will be structured with a column or row block for each impairment group in the order (Mild Renal Impairment, Moderate Renal Impairment, Severe Renal Impairment, Matched Controls) and will be annotated with the total population size relevant to that table/impairment group, including any missing observations. More details will be provided for reporting pharmacokinetic results in Section 10.

Estimates and CIs will be utilized rather than formal hypothesis tests.

No formal hypothesis tests are planned for safety analyses, but safety data will be collected and analyzed.

